Rules, precedingly referred to as 'business rules', were developed for in App notifications that follow the guidance of the RTA/RTS protocols for progression through the stages (Appendix 1.1) Symptoms, self reported stages and activities are measured daily in the morning, afternoon and evening. A summary of these surveys is found in appendix 1.2. The home screen of the App (appendix 1.3) summarizes the next survey time, current stage of return to school and activity the youth is reporting that day and the activity minute goals (based on their stage of recovery) and how many activity minutes are completed. Icons at the bottom direct users to 1) a summary page that will show this information as well as a graph of their current symptoms, 2) a charts page which has several graphs of their progress (symptoms, stages, heart rate and activity minutes), 3) resources including the CanChild guidelines for concussion recovery, symptom strata (or the type of recovery pattern they may be following), the playsafe cards for individual sport specific strategies and a list of activity suggestions for each stage of recovery and 4) a contact us page which gives the Research Team [contact] and Principal investigator contact info as well as a form for troubleshooting help. When youth fill out the surveys, if 2 or more symptoms are worse, a pop up option of texting or emailing the participant's parent appears (appendix 1.3) Notifications are also sent to youth who exceed their activity goals and the Back2Play App will send a cautionary message "You are doing too much!" if their heart rate goes above 180. Encouraging notifications are also programmed with business rules if participants stay in the same stage for extended periods or if their symptoms get worst.

A complimentary App was developed by [name] of our investigator team. This Brain Games App was designed to screen some typical neurocognitive functions affected by concussion. There are 5 "games" that take about 10 minutes to complete. These include 1)

finger-tapping, 2) divided attention, 3) memory for designs, 4) tracing and 5) face match. An 'in App notification' is triggered by the youth recording a progression in their RTS stage. "Let's do a brain teaser! Sign into The Back2Play Brain Games App for your brain game then complete your symptom survey!" If the challenging tasks result in increased symptoms, The App notifies them "The brain game can be hard, stay at this stage if you need too!"

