8. DESIGN

Phase 3 of this study has both quantitative and qualitative components. The aims of the qualitative components of the study are to determine if participants liked using The App, and if their experiences of using it helped their recovery from concussion. In addition, qualitative data will be used to review any improvement suggestions to The App before commercialization. Using both qualitative and quantitative research methods we will explore

the usability of The Back2Play App components under consideration for the final version of the App to be commercialized.

Primary Research Outcomes

To assess:

- Risk for repeat head injuries within three months of study completion (3-6 months after injury)
- Duration of symptoms: Time to symptom resolution from date of injury

Secondary Research Outcomes

To assess:

- 1) The frequency of symptoms using PCSS.
- 2) Time to return to activity and time to progress through the 6 stages of RTA
- 3) Perceptions of the platform by parents and youth.
- 4) Accuracy of the algorithm embedded in the background of The App classifying the participant's stage of recovery

Measures

Symptoms

Concussion symptoms will be assessed on The Back2Play App for those randomized to The App group and via REDCap for those randomized to Usual Care. A modified version of the PCSS (consisting of 22 symptoms) will be completed by youth in both groups. The Likert scale was modified to detect the presence of symptoms rather than symptom severity. Symptom data will be collected 3x/day for participants using The Back2Play App and every 24 hours for participants in the Usual Care group.

Cognitive Activity

Cognitive activity will be assessed using a modified version of the scale developed by Brown et al. Participants in both groups will be asked to complete this scale once per day through REDCAP which will appear as follows:

"Please rate 1-5 what you've been doing today"

- 1- None- No reading, homework, text messaging or screen time (T.V., cell phone), can talk on phone
- 2- Minimal- 15 minutes of screen time or schoolwork 2x daily. Socialize with 1-2 friends, no longer than 30 minutes,
- 3- Moderate- Homework in 15 minutes blocks for a maximum of 45 minutes. Screen time/T. V in 15-minute blocks, for up to an hour daily.
- 4- High- Complete as much homework as tolerated. 1 test/week or tests with accommodation (i.e. longer time to write), less reading, homework and screen time than normal
- 5- Full- no restrictions to cognitive activity

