Appendix 1.1 Business Rules for In-App Notifications

Progression through the CanChild RTA/RTS Guideline

- 1. Participants cannot enter RTA Stage 4 until they have completed RTS Stage 1-3
 - o If the participant reports RTA Stage 4 when they are in RTS Stage 1 or 2 they will receive the message "Stage 1, 2 and 3 come before RTA Stage 4!"
- 2. Participants must complete RTS Stage 5 (Full Return to School) before they can enter RTA Stage 4.
 - If the participant reports RTA Stage 4 or 5 when they are in RTS Stage 3 through 5, they will receive the message "You should complete RTS Stage 4-5 before RTA Stage 4-6".
- 3. Participants will be recommended to move to Stage 2 of RTS after 7 days
 - o If the participant reports RTS Stage 1 for 7 days, they will receive the message "You reported being in Stage 1 for 1 week, time to move to Stage 2!"
- 4. Participants will be recommended to move to Stage 3 of RTS after 14 days
 - o If the participant reports RTS Stage 2 for 14 days, they will receive the message "You reported being in Stage 2 for 2 weeks, time to move to Stage 3!"
- 5. Once in RTS Stage 3, participants cannot move back to Stage 2.
 - o If the participant reports RTS Stage 3 and moves back to RTS Stage 2, they will receive the message "Once your reach RTS Stage 3, you should not return to RTS Stage 2".

- 6. Participants are recommended to complete RTA and RTS Stage 1-3 together.
 - o If the participant reports RTA Stage 3 while in RTS Stage 1 or 2, they will receive the message "Remember, RTS and RTA Stage 1 to 3 should go together!"
- 7. Participants will be cautioned when they try and skip a stage
 - o If the participant skips from RTS Stage 2 to RTS Stage 4, they will receive the message "You forgot RTS Stage 3, we recommend you log this stage first!"
- 8. Participants will be cautioned when they try to move back a stage.
 - o If the participant moves back a Stage i.e., RTS Stage 5 to Stage 4, RTA 5 to Stage 4 they will receive the message "*Are you sure you want to move back a stage?*"
- 9. Participants cannot progress to a new stage of RTA/RTS if 2 or more symptoms worsen
 - o If the participant reports that 2 or more symptoms worsen (from morning to evening survey), **and** the participant attempts to progress to a new stage, they will receive the message "We recommend you do not progress to a new stage and inform a parent of your symptoms".

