- 10. Participants cannot progress to a new stage of RTA/RTS if their total number of symptoms increases by 2.
 - o If the participant reports an increase in symptoms by 2 (from morning to evening survey) **and** the participant attempts to progress to a new stage, they will receive the message "We recommend you do not progress to a new stage and inform a parent of your symptom".

CanChild RTA/RTS Symptom Strata

- 11. Participants will be classified to Strata A (Symptom Free within 48 hours after Injury) if their initial symptoms disappear within 24 hours or after 24-48 hours a participant reports ≤ 2 symptoms.
 - o If symptoms worsen, a participant can transition to Strata B.
 - o If the participant reports that their symptoms disappear within 24 hours, they will receive the message "Take at least 24 hours for each Stage as you complete the guidelines".
- 12. Participants will be classified to Strata B (Symptom Free/Symptoms decreases within 1-4 weeks post injury) if the report > 2 initial symptoms at 50 hours and continue at > 2 for 1 week (168 hours) up to 4 weeks. If the child's symptoms decrease, but are still >2, the child should remain in stratum B.
 - o Once a participant is in Strata B, they can never go to Strata A.
 - o If a participant is in Strata B and progressing through Stages within 2 days, but symptoms are getting worse, the child should take longer to progress through the stages.
 - o If > 2 Symptoms for a month, move the participant to Strata C

- o Recommendation: "Take at least 48 hours for each Stage as you complete the guidelines".
- 13. Participants will be classified to Strata C (Symptomatic for more than 4 weeks) if they report ≥ 2 initial symptoms for ≥ 4 weeks, or if the participant has been in Strata B for 1 month.
 - Once a participant is in Strata C, they can never go to Strata A or B.
 - o Recommendation: "Take at least 1 week for each Stage as you complete the guidelines".

Increasing or Worsening Symptoms

- 14. Participants will be reminded to share their symptoms with their parents if their number of symptoms increases by 2
 - o If the participant reports 2 or more symptoms new symptoms, they will receive the message "We recommend you inform a parent of your symptoms".
- 15. Participants will be reminded to share their symptoms with their parents if 2 or more symptoms worsen.
 - o If the participant reports 2 or more symptoms worsen, hey will receive the message "We recommend you inform a parent of your symptoms".

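### Only in the App arm do the symptom answers behind time to symptom resolution also trigger messages, pacing advice and parent prompts, so reporting can differ by arm for reasons other than recovery

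*Combined protocol and SAP*

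**What the plan says.** Section 8 (Primary Research Outcomes) lists "Duration of symptoms: Time to symptom resolution from date of injury". Under Measures, Symptoms, the source differs by arm: "Concussion symptoms will be assessed on The Back2Play App for those randomized to The App group and via REDCap for those randomized to Usual Care". Both arms use a 22-item list, altered so that it records only whether a symptom is there: "The Likert scale was modified to detect the presence of symptoms rather than symptom severity". The frequency differs too: "Symptom data will be collected 3x/day for participants using The Back2Play App and every 24 hours for participants in the Usual Care group". Section 6 states that neither participants nor researchers can be blinded.

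Appendix 1.1 sets out what the App does with the answers.

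- Rules 9 and 10 concern progression. Rule 9 reads "Participants cannot progress to a new stage of RTA/RTS if 2 or more symptoms worsen", and rule 10 applies the same to an increase of two symptoms. The action given for both is a message recommending against progression and suggesting that a parent be told.
- Rules 11 to 13 assign strata by how long symptoms last. The advised minimum per stage is 24 hours in Strata A and 48 hours in Strata B. In Strata C the advice is "Take at least 1 week for each Stage as you complete the guidelines". Youth cannot return to a faster stratum.
- Rules 14 to 16 send parent reminders and a slow-down message when symptoms increase or worsen. The trigger text of rule 17 gives praise when two or more symptoms are logged as better.

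Section 2 (Back2Play App) adds that "if 2 or more symptoms are worse, a pop up option of texting or emailing the participant's parent appears".

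For Usual Care, section 7 describes a survey emailed by REDCap every 24 hours. No response to the answers is described. Section 9.5 plans survival curves and Cox regression, with no sensitivity analysis for differences in reporting.

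**The concern.** An efficacy outcome should be measured so that giving a particular answer has the same consequences in both arms. Here the App is both the treatment and, for its own arm, the measuring instrument. A youth in that arm learns that some answers bring cautions, a prompt about parents or a slower advised pace, and that others bring praise. A youth in Usual Care sees no such response.

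The introduction reports that youth had difficulty following return protocols, so a motive to shade answers is plausible, although nothing in the documents measures it. If reporting shifts for this reason, the recorded resolution date moves without any change in recovery. Cox regression takes the recorded date as the event time and has no information with which to tell the two apart.

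**Working it through.** **Plan's own figure.** No sample size is given for time to symptom resolution. Section 3 sizes the trial on repeat head injury. At two-sided 0.05 and power 0.80, 16% against 2% gives 130 in total by the pooled formula (stated: 128). Allowing for 20% loss, 128 / (1 − 0.20) = 160, as stated. The 64 per arm used below is 128 / 2.

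**Which rules respond to what.**

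| Rules | Fire on | Response |
|---|---|---|
| 9, 10 | worsening or two added symptoms, morning to evening | advice not to progress, tell a parent |
| 14–16 and parent pop-up | two or more added or worse symptoms | parent prompt, slow-down message |
| 17 | two or more symptoms better | praise |
| 11–13 | symptoms persisting past about 48–50 hours, or 4 weeks | slower advised pacing, one way |

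Only rules 11 to 13 react to symptoms that are merely still present, so they bear most directly on when a youth reports resolution. They can do so only before each threshold. The other rules bear on whether deterioration or improvement is logged. The Usual Care column for every row would be empty.

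**Illustration of size.** The documents give no under-reporting rate, so the rates below are assumptions. The set-up has no true effect, 64 per arm, exponential recovery with median 28 days, daily recording, a 90-day cap and a log-rank test, counting z > 1.96 in favour of the App. The curve leaves 0.5^(30/28) = 48% symptomatic at 30 days (section 2 cites 59% and 47% at one month) and 0.5^(90/28) = 11% at 90 days (section 2 cites 14% and 13%).

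| App youth reporting early | Reported time / true time | Fall in mean time before the cap | Trials with false App benefit |
|---|---|---|---|
| none | 1 | 0 | about 2% (nominal 2.5%) |
| 25% | 0.75 | 0.25 × 0.25 = 6.25% | about 5% |
| 25% | 0.5 | 0.25 × 0.5 = 12.5% | about 12% |
| 50% | 0.75 | 0.5 × 0.25 = 12.5% | about 10–13% |
| 50% | 0.5 | 0.5 × 0.5 = 25% | about 36–38% |

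Section 3 regards a 10% decrease in recovery time as of interest. The third and fourth rows already exceed that.

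**Second curve.** A Weibull was fitted to 59% symptomatic at 30 days and 14% at 90 days.

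- Shape = ln(ln 0.14 / ln 0.59) / ln 3 = 1.197; median 37.7 days.
- If 20% or 30% of App youth report at half the true time, false App benefit occurs in 10% or 20% of trials.
- If all report 10% early, the apparent hazard ratio for recovery is (1/0.9)^1.197 = 1.13, and false benefit occurs in 9% of trials.

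**Opposite direction.** On the same Weibull curve, if App surveys delay recorded resolution by 10% or 20%, the simulated hazard ratio is 0.87 or 0.79, against the App.

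**The case against.** A reader might infer that an App youth gains freedom by logging no symptoms, and that the trial is therefore biased in the App's favour. The documents do not support that.

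- No lock is described. The progression rules end in a recommendation, stage is self-reported, and the parent pop-up is optional. An eager youth can ignore the message without falsifying symptoms.
- Rules 9, 10 and 14 to 16 fire on worsening or added symptoms. Stable symptoms trigger none of them.
- The strata are one-way. Once a youth is in B or C, logging no symptoms does not restore faster pacing. Enrolment is open through the first month after injury, so some youth may be past the first threshold at entry.
- Three surveys a day give more chances to record a symptom, and the App's daily survey (Appendix 1.2) brings up the previous day's symptoms. Both could make App youth look slower to recover.

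All four points stand. They remove any claim about direction, but not the arm-specific consequence of answering.

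The follow-up interview (Appendix 1.6) asks everyone about remaining symptoms. It is at most a partial check: it is timed from reported resolution (or held at 3 months), run by unblinded staff, and not named as the outcome source. Section 1 calls Phase 3 a feasibility trial, but it also sets out to compare effectiveness and names this outcome as primary.

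The simulated figures rest wholly on assumed rates, and the mildest scenario gives only about 5%.

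**Conclusion.** The structural point holds. In one arm only, the answers that supply a self-reported, unblinded primary outcome also draw responses from the intervention, and neither the planned analysis nor the interview corrects for it. Differential reporting is a risk here, not a demonstrated effect, and its net direction and size are unknown.

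If the App's responses lead a quarter of its users to report resolution at 0.75 or 0.5 of the true time, false App benefit rises from a nominal 2.5% to about 5% or 12%. If the heavier survey schedule dominates, the bias runs against the App. These figures assume no true effect, 64 per arm, median 28 days and a 90-day cap. The change below is a cheap improvement worth making; the point does not show that the trial's result would be wrong.

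**What to change.** Take the resolution date in both arms from one identical once-daily 22-item yes/no list sent by REDCap, on the same schedule, with no link to the App's rules. Tell App youth that these answers do not drive the App. State, identically for both arms, which answers on this list count as resolution, since the plan does not say. Keep the in-App surveys for guidance, and use them only in a sensitivity analysis of the resolution date. No App feature or clinical rule changes.

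The delivery route must be confirmed. Section 8 says of the cognitive scale that "Participants in both groups will be asked to complete this scale once per day through REDCAP", whereas Appendix 1.2 puts that scale in the App's evening survey. These need reconciling. If section 8 governs, the list can be attached to an existing daily form. If Appendix 1.2 governs, App youth need a new daily REDCap contact.

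The cost is a protocol amendment and about a minute of extra survey a day for App youth. The form already exists for Usual Care. Reporting stays unblinded, and a youth who under-reports in the App may do the same in REDCap. The change removes the arm-specific consequence of answering and the difference in survey frequency, but not every source of reporting bias.

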9.5. DATA ANALYSIS PLAN

The recordings of online consent (Zoom), for Phase 3, will be stored on a study computer and saved to a secure password encrypted server. As described above, participants will be asked to complete the (SUS). The SUS yields a single number representing a composite measure of the overall usability of the system being studied. Adjustments and modifications to The Back2Play App will be made before commercializing the product.

We will collect and report descriptively all demographic information, injury-related data (type, mechanism of injury, numbers of injuries), youth premorbid health history. Descriptive statistics such as means, medians, and frequencies will be reported where appropriate. Baseline comparisons will be performed between those that use The App and those whose recovery involved Usual Care with variables of mechanism of injury, age, sex, school performance and concussion history. These variables will be-analyzed using Pearson Chi Squared Cross Tabulations, T-Test and ANCOVA, to ensure the groups are similar. We will also evaluate agreement of the algorithm with the self-reported stage of recovery participants input using these same statistics.

The dichotomous variable, repeat injuries (coded as yes or no), will be analyzed using multivariate logistic regression and resulting odds ratios to determine if using The Back2Play App decreases risk of repeat injury. Confounders of age, gender, number of symptoms, time since last injury and comorbidities of premorbid mental health issues or learning disabilities will be examined as to their potential impact on outcomes. Many of these variables will be correlated with each other and these correlations will need to be examined carefully before they are entered into the analyses.

Time to symptom resolution will be analyzed using survival curves with Multivariate Cox regression analysis. Cox regression (also called proportional hazard models) is a method of survival analysis that models the time until some event as a function of either continuous or categorical predictors, allowing for the fact that not all subjects will experience the events of interest and that they will occur at different times.

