Appendix 1.2 In-App Surveys

Morning Assessments	MidDay	Evening Assessments	
	Assessments		
Stage 1- First assessment			
Post-Concussion Symptom Scale (Modified for App and hereon called Initial Symptom Survey) "How are you feeling this morning? Are	Global: "How are you doing today?" question. If response is "Bad" present symptom survey.	Cognitive Scale: "Please rate 1-5 what you've been doing today" 6- None- No reading, homework, text messaging or screen time (T.V., cell phone), can talk on phone	
you experiencing" 1. A headache: Y/N? 2. Nausea: Y/N? 3. Balance Problems: Y/N? 4. Dizziness: Y/N? 5. Fatigue: Y/N? 6. Drowsiness: Y/N? 7. Sensitivity to light: Y/N? 8. Sensitivity to noise: Y/N? 9. Irritability: Y/N? 10. Sadness: Y/N? 11. Nervousness: Y/N? 12. Feeling more emotional: Y/N?	"Please select what cognitive activities you have been doing today" 1. Socialize with friends 2. Talk on the phone 3. Text friends 4. Watch a short video/T.V. 5. Rest in bed 6. Light Reading 7. Other	 7- Minimal- 15 minutes of screen time or schoolwork 2x daily. Socialize with 1-2 friends, no longer than 30 minutes, 8- Moderate- Homework in 15 minutes blocks for a maximum of 45 minutes. Screen time/T. V in 15-minute blocks, for up to an hour daily. 9- High- Complete as much homework as tolerated. 1 test/week or tests with accommodation (i.e. longer time to write), less reading, homework and screen time than normal 10- Full- no restrictions to cognitive activity 	
13. Feeling Slowed down: Y/N? 14. Mentally foggy: Y/N?		"Please select what physical activities you have done today"	

15. Difficulty concentrating: Y/N?	1. Get up and dressed
16. Difficulty remembering: Y/N?	2. Chores/Housework
17. Visual problems: Y/N?	3. Going for a walk outdoors
18. Confusion with directions/tasks:	4. Other
Y/N?	
19. Move in a clumsy manner: Y/N?	"Daily Symptom survey"
20. Answer questions more slowly than	
usual: Y/N?	
21. Neck pain: Y/N?	
22. Trouble sleeping: Y/N?	
"What Stage of the RTS protocol are	
you in? Select: 1, 2, 3, 4, 5"	
"What Stage of the RTA protocol are	
you in? Select: 1, 2, 3, 4, 5"	

Stage Two			

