Appendix 1.6

Follow Up Interview

Ask Everyone:

Tell me about where you are in recovery from your concussion.

Prompts:

Are you still experiencing any symptoms?

Did you hit your head again during your recovery?

If yes did it increase symptoms and how did it affect your recovery?

Are you back fully to school and sport?

Do you feel back to your previous self?

Are there any other therapies or treatments that you tried during your recovery from concussion? Prompts:

Medications, physio, chiro, other medical professionals

Ask App users:

Tell me about your experience in using the App during your recovery from concussion.

Follow Up questions:

Did you receive notifications from the App-give me some examples

Did you do the surveys on your watch or phone?

Did you ever use data or mostly Wi-Fi?

Did you ever forget to charge the watch? How often?

Did you agree with the guidance you were given re: activity or stage levels? (%)

Did you find the App helpful at all in your recovery-how so?

Did you like the App?

Follow up questions:

What were the best features of the App

Were there features you didn't use that much

Were there things that you didn't like or found annoying

How could we make it better?

Ask Usual care group

What was involved in your care and follow up with your concussion?

Were you given some sort of guidelines to follow to return to play and school?

What format were they in?

Did you seek extra treatment or help?

Did you feel you understood how to get better and get back to activities and school after your concussion?

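### The yes/no symptom items have no pre-injury reference, so youth with long-standing symptoms may be recorded as unresolved on the time-to-resolution primary outcome

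*Combined protocol and SAP*

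**What the plan says.** Section 8 (Primary Research Outcomes) lists "Duration of symptoms: Time to symptom resolution from date of injury" beside repeat head injury. The instrument is a modified 22-item Post-Concussion Symptom Scale, used in both groups. Under Measures, Symptoms, the plan states: "The Likert scale was modified to detect the presence of symptoms rather than symptom severity".

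Appendix 1.2 gives the in-App wording. The youth is asked what they are experiencing that morning and answers yes or no. Items include "10. Sadness: Y/N? 11. Nervousness: Y/N", "15. Difficulty concentrating: Y/N" and "22. Trouble sleeping: Y/N", as well as fatigue and irritability. No item refers to the state before the injury.

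Some pre-injury information is planned. Section 9.5 collects and describes "injury-related data (type, mechanism of injury, numbers of injuries), youth premorbid health history", and lists "comorbidities of premorbid mental health issues or learning disabilities" among the confounders to be examined. Appendix 1.6 has the interviewer ask every participant, "Do you feel back to your previous self".

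Section 4 excludes diagnosed developmental disability, but not mental health, learning or sleep problems. Section 7 ends symptom follow-up 2 days after resolution, or at 3 months. The protocol gives no operational definition of resolution.

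**The concern.** Several of the 22 items are common complaints that need not come from a concussion, and section 9.5 expects some participants to have premorbid mental health or learning problems. A severity scale could show such a youth falling back to a usual level. A yes/no item cannot: the answer is yes before the injury, yes after it, and yes once the concussion has cleared.

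This is related to the missing definition of resolution but separate from it. A definition can be written at any time before analysis. Item-level pre-injury status that was not asked for at enrolment can only be recalled months later.

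At stake is one primary outcome. Affected youth contribute no event and stay in the risk set until censoring. The resulting curve mixes pre-injury health with recovery from the injury.

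**Working it through.** **1. The plan's own figure.** The sample size (section 3) uses repeat head injury, two-sided 0.05, power 0.80. With the pooled two-proportion formula, n per arm = [1.96·√(2p̄q̄) + 0.842·√(p₁q₁ + p₂q₂)]² / (p₁ − p₂)²:
- 16% vs 2%: 65 per arm, total 130 (stated 128).
- 37% vs 13%: 50 per arm, total 100 (stated 100).
- 128 / 0.80 = 160 (stated 160).

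The figures reproduce, allowing for rounding, but they say nothing about power for symptom resolution.

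**2. Can any planned item separate an old symptom from a new one?**

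| Source | What it gives | Why it does not suffice |
|---|---|---|
| Premorbid history, section 9.5 | Person-level conditions | Does not show whether today's yes to an item is new. Adjustment cannot turn a censored time into an event. |
| Closing interview, Appendix 1.6 | One global answer | Asked once at the end and not linked to the outcome, so it cannot date recovery. |
| Better/worse logging, Appendix 1.1 rules 9 and 14–17 | Change in symptoms | Drives App notifications, has no stated pre-injury reference and is not described for Usual Care. |

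**3. How many persistent items block resolution?** Under a zero-symptom rule, one. The only count threshold in the documents is the App's Strata A rule (Appendix 1.1, rule 11: two or fewer), which is not an endpoint definition. If it were used, three or more would be needed.

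**4. Illustrative size under a zero-symptom rule.** Inputs: 128 evaluable (section 3); 86% otherwise resolved at 3 months (100% minus the 14% in section 2). Assumptions: a share f of youth with at least one persistent pre-existing item, independent of true recovery, and a hazard ratio (HR) of 1.5 or 1.75.

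Events = 128 × 0.86 × (1 − f). Schoenfeld power = Φ(√(events/4) × ln HR − 1.96). For f = 0 and HR 1.75: √(110.1/4) × 0.5596 − 1.96 = 0.976, so power is 0.835.

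Schoenfeld's formula counts lost events only and holds the HR fixed. Youth who cannot register resolution also stay in both risk sets and pull the observed HR towards 1. I therefore simulated log-rank tests: 64 per arm, exponential times, 86% pooled resolution at 90 days when f = 0, 10,000 runs per setting.

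| f | Resolved at 3 months | Events | Schoenfeld, HR 1.75 | Simulated, HR 1.75 | Schoenfeld, HR 1.5 | Simulated, HR 1.5 |
|---|---|---|---|---|---|---|
| 0 | 86% | 110 | 84% | 83% | 57% | 57% |
| 10% | 77% | 99 | 80% | about 62% | 52% | 37% |
| 30% | 60% | 77 | 69% | about 32% | 43% | 19% |
| 40% | 52% | 66 | 62% | 23% | 38% | 15% |

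In the simulation, a true HR of 1.75 was estimated on average at about 1.59 when f = 10% and 1.41 when f = 30%. Most of the loss is therefore dilution rather than missing events.

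**5. At the plan's own effect size.** Section 3 names a 10% shorter recovery time as of interest. Under exponential times that is HR = 1/0.9 = 1.11. Schoenfeld power is then about 8% at 110 events and 7% at 77, so the outcome is underpowered for that effect with or without this problem.

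**The case against.** The strongest reply is that the plan does address pre-injury health. It collects premorbid history, names mental health and learning problems as confounders, and asks about the previous self at the end. A reader might infer from the yes/no format that no pre-injury status is collected at all. That is wrong: only item-level status is missing from what is shown. The REDCap surveys and the premorbid-history form are not reproduced, so absence from them cannot be asserted.

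A reader might also infer that affected youth can never be seen to recover. The documents do not support that either. It needs a zero-symptom rule, which is not stated, and a yes on every qualifying day. Sadness or poor sleep can vary from day to day, and some youth may answer only for symptoms they attribute to the concussion.

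The sizes are also open to challenge. The shares and hazard ratios are assumed. If pre-existing items are concentrated in the 14% who stay symptomatic anyway, or if that 14% already includes them, the loss is smaller. The 14% comes from a cited cohort timed from injury, whereas this trial enrols youth who are still symptomatic up to a month after it.

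All of this limits the strength of the claim. The gap itself remains: nothing shown can identify, or date, a return to the pre-injury level on an item.

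**Conclusion.** The point holds in this form: youth with long-standing symptoms **may** be recorded as unresolved, because the items behind a primary outcome have no pre-injury reference. How many are affected depends on a resolution rule that the plan does not give and on a prevalence that the documents do not report. With a zero-symptom rule, an assumed 10% share and an assumed HR of 1.75, power drops by about 20 percentage points. That is an illustration, not an estimate.

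Bias between arms is a further inference that the documents do not support. Allocation is 1:1 and pre-existing symptoms should balance on average, although chance imbalance is possible with 160 youth. The expected harm is fewer events, an HR diluted towards 1 and an outcome that is harder to interpret. Repeat head injury, on which the trial was sized, is not directly measured by these items. The change is worth making before enrolment because the missing information cannot be reliably rebuilt later.

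**What to change.** Make the same three changes in the App and in REDCap.

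1. At the initial survey, preferably before allocation is revealed, ask once for each endorsed item whether it was present before the injury: *no / yes, about the same / yes, but worse now*.
2. Word the repeated daily items as *new or worse than before your injury*. Step 1 alone is not enough: a youth who answered *worse now* and then returned to the usual level would still truthfully answer yes to an unqualified item.
3. Base the resolution count on new-or-worse items, and state the count that defines resolution. Use the initial answers for a sensitivity analysis that excludes, or stratifies by, youth with pre-existing items.

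**Cost.** One extra tap per endorsed item at a survey that both arms already complete with a Research Assistant, a wording change in two systems, and a few lines in the outcome definition. Asking before allocation means placing the initial survey ahead of randomisation; section 6 randomises once consent is obtained. The App's notification rules also count symptoms, so the team must decide and document which wording those rules read. The main weakness is that pre-injury status is retrospective self-report, and the daily answers come from unblinded youth.
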